Randomization- Patients will be randomized with a probability 2:1 of receiving one of the exercise interventions as compared to usual medical care. The unbalanced design was chosen because we expect a larger functional recovery in both exercise groups as compared to the usual care group requiring higher sample size in these two arms to be able to detect smaller differences between them compared to larger differences from the usual care arm. The study coordinator will carry out the randomization through a web-based computer system at the end of baseline visit, thereby preserving allocation concealment. We

Table 1- Time points and outcome measures of the study	Baseline	Month 3 and 6	Call Month 1.5 & 4.5
Aim 1			
Physical Function (WOMAC-PF & performance tests)	x	x	
Physical Activity (SWA & CHAMPS)			
Aim 2			
Demographics and Biomedical	x		
Medication	x		
Comorbidities	x		
Psychosocial (fear, anxiety, self-efficacy, depression, coping)	x	x	
Physical Impairments (pain, range of motion, muscle strength)	x	x	
Exploratory Aim			
Adverse Events		x	x
Attrition		x	
Adherence with intervention		monitored each visit	
Co-Interventions		x	x

PRINCIPAL INVESTIGATOR (LAST, FIRST, MIDDLE): [name]

will use an adaptive randomization to minimize imbalances in important prognostic variables at baseline including gender, age, BMI, physical function, and knee range of motion. The minimal sufficient balance algorithm⁵² will be used as this method accommodates both categorical and continuous variables. Our data center staff have experience creating this type of randomization algorithm within the framework of the clinical trial database, necessary because the allocation is assigned based on the instantaneous imbalances instead of being generated as a fixed list prior to the beginning of the trial. [name] will monitor randomization and imbalances monthly.

OUTCOMES- The outcomes of this study are entirely patient-centered and selected directly from patient input during structured interviews. They include a broad range of measures as described in Table 1.

Physical Function

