- **Adverse Events-** We will capture information on (1) changes in knee pain, swelling, and stiffness; (2) difficulty to bear weight on the surgical leg; (3) falls; (4) if subject has been hospitalized or disabled (> ½ day in bed or required to cut back on routine activities), and; (5) if subject had a TKR on the other knee. For information on falls we will ask subjects if they have had any falls using a 2-3 minute questionnaire developed at the Pittsburgh Pepper Center. One-week test-retest reliability (Kappa) was established as 0.89 in a sub-sample of 43 participants enrolled in a Pepper Center observational cohort study of older adults ([name] unpublished data). Falls will be defined as unintentionally coming to rest at a lower position. In this study serious adverse events (SAEs) are defined as hospitalization, death, or permanent disability. Adverse Events (AEs) are defined as exercise-related discomforts that remains for 3 days or longer (e.g., muscle and joint soreness/pain), minor injuries (e.g., strains, sprains), and non-injurious falls. Transient side effects are defined as complaints of increased pain, stiffness, or muscle weakness for periods of 2 days or shorter. We will compare the measures of harm such as adverse events and attrition by treatment interventions. If they differ between groups, they will be used as a covariate in the final outcome analysis.

We will also monitor attrition, adherence and co-interventions:

- **Attrition** is defined in this study as the number of patients dropping out of the study in each group.
- **Adherence** to intervention will be estimated by the proportion of sessions attended in each group and the proportion of patients missing each session. Adherence to the individualized outpatient exercise will be recorded by the physical therapist. Adherence to the group exercise classes will be obtained from reports generated by the community centers.
- **Co-interventions** will be queried during every assessment. Some subjects could decide to seek additional treatment options while enrolled in the study. We will ask about additional treatment sought (e.g., seeking specialized care), and participation in exercises besides the ones prescribed by the study. If the subject participated in additional exercises, we will record the frequency, duration, and type of the exercise and will analyze these data for their potential effect on the primary outcome.

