For Aim 2, we plan to assess predictors of response based on a minimum change score of 20% in BOTH the WOMAC-PF and the composite score of functional performance at 3 months, thus yielding a binary outcome. For this aim, we will have a combination of those initially randomized to one of the exercise arms and those in the usual care group who were later randomized to the exercise arms for a total of approximately 200. If the expected response rate ranges between 50% and 60%, we would be able to detect an odds ratio of 2.2 to 2.4 with 80% power assuming a binary predictor with 50% split in the sample. In addition, with approximately 100 responders, we will be able to accommodate 9 predictors in the multiple logistic regression based on rule of thumb guidelines for sample size in logistic regression (min of response/nonresponse/ (#predictors+1) \geq 10).

Data Analysis

[name] will oversee data analyses. We will evaluate the statistical properties of baseline and follow-up outcome measures, including potential outliers, normality and missing data. Measures of central tendency (means, medians, other percentiles) and dispersion (standard deviations, ranges) will be computed for continuous variables, whereas frequency distributions will be calculated for categorical data. Distributions of baseline characteristics will be compared between groups to assess effectiveness of randomization, and statistical or clinical differences will be adjusted in the analyses. Data transformations may be applied if needed and guided by clinical meaningfulness.

Hypothesis 1.1 - Subjects in Groups 1 and 2 will demonstrate better physical function as compared to Group 3.

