The primary outcome of this aim is the WOMAC-PF at 3 months.⁹¹ This analysis will use an intention-to-treat approach. We will analyze this aim using contrasts from a linear mixed models analysis for 3 and 6 month function controlling for baseline function and the randomization covariates (age, gender, BMI, physical function, ROM). We will first explore the intervention by time interaction, and then proceed to a main effects model with only group and time. Our primary interest is the 3 month comparison between the clinic-based individual outpatient exercise and the community-based exercise groups. The linear mixed models allow us to maximize the number of individuals used for the analyses as a person can contribute information at both time points, or just one time point. This analysis is advantageous to conducting a simple baseline adjusted ANCOVA at 3 months because persons missing 3 month data would not be included. The linear mixed model “borrows” information pertaining to the relationship between the 3 and 6 month outcomes such that persons missing either (but not both) can still be used in the analyses. To test if the improvements in outcomes are sustained, we will use contrasts from the linear mixed model at 6 months. For missing 3 and 6 month outcomes see missing data section.

For the battery of performance-based tests we will perform the analyses as described above, one for each measure. For these secondary outcomes we will use Hochberg’s step-up procedure to control the experiment-wise Type I error rate ($\alpha=0.05$),⁹² which otherwise would be inflated due to the multiple endpoints. Hochberg’s procedure is more powerful than Bonferroni adjustment and performs well when the number of endpoints is small and correlated with small to mid-size correlations. For this outcome we will also perform analysis using a composite score formed with unit-weighted z scores of constituent tests to provide a more stable measure of the subjects’ underlying functional performance.⁹³

Hypothesis 1.2- Subjects in Groups 1 and 2 will demonstrate increased physical activity as compared to Group 3.

Adjusted analysis for the outcome of physical activity will parallel the analyses described above for performance-based physical function. The outcomes of this hypothesis are real-time physical activity data captured by the SWM and self-reported physical activity from the CHAMPS questionnaire

PRINCIPAL INVESTIGATOR (LAST, FIRST, MIDDLE): [name]

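### Adverse events and attrition arise after randomisation, yet the plan would add them as outcome covariates whenever the arms differ

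*Combined protocol and SAP*

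**What the plan says.** - **Capturing Potential Harm of Interventions, Adverse Events:** "We will compare the measures of harm such as adverse events and attrition by treatment interventions". The next sentence is the rule at issue: "If they differ between groups, they will be used as a covariate in the final outcome analysis". The section does not say which outcome model is meant, and it sets no criterion for a difference.
- **Same section, definitions:** "Adverse Events (AEs) are defined as exercise-related discomforts that remains for 3 days or longer"; minor injuries and non-injurious falls also count. Attrition "is defined in this study as the number of patients dropping out of the study in each group".
- **Table 1** ("Time points and outcome measures of the study"): adverse events and attrition have no baseline entry. Adverse events are recorded up to month 6.
- **Data Analysis, opening paragraph:** for baseline characteristics, "statistical or clinical differences will be adjusted in the analyses". This extends adjustment to baseline differences and no further.
- **Hypothesis 1.1:** "This analysis will use an intention-to-treat approach". The linear mixed model is described as "controlling for baseline function and the randomization covariates (age, gender, BMI, physical function, ROM". The comparison of primary interest is clinic-based versus community-based exercise at 3 months.
- **Exploratory Hypothesis:** attrition and adverse events are expected to be lower in Groups 1 and 2 than in Group 3. For adverse events, clinical judgement is ranked above testing.

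**The concern.** An intention-to-treat contrast compares the arms as randomised. Adjusting for baseline variables leaves that target intact. Adjusting for something that happens after randomisation, and that the arm can influence, does not.

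There are two routes to a shift. If events themselves worsen (or accompany better) WOMAC-PF, part of the arm's effect runs through them and is removed. If events and WOMAC-PF share an unmeasured cause, patients with the same event status are no longer comparable between arms, and the contrast moves even when events do nothing to function.

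The rule applies only when the arms differ in events, which is exactly when adjustment moves the contrast. Whether they differ is left to judgement once the data are in hand. Two analysts following this document could report different effects as the trial result.

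**Working it through.** **1. The plan's own figures.** Inputs from the Sample Size section: SD 7.7, two-sided alpha 0.05, 86 per exercise arm, 43 in usual care.
- Exercise v exercise: SE = 7.7 × √(1/86 + 1/86) = 1.174 and 3.3/1.174 = 2.81. Power is 80.2% (normal) or 79.8% (noncentral t). The plan states 81%, so this is reproduced.
- Usual care v one exercise arm: SE = 7.7 × √(1/43 + 1/86) = 1.438 and 5.2/1.438 = 3.62. Power is 94.8%, where the plan states 80% (reached at about 4.1 points). That is a separate matter; the computed value is the starting point below.

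**2. Formula.** For a linear model with an event indicator added:

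adjusted contrast (A − B) = total contrast − γ × (p_A − p_B)

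Here p is the proportion with an event, and γ is the within-arm WOMAC-PF difference between patients with and without one. Higher WOMAC-PF is worse, so a negative shift flatters the arm with more events.

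**3. Illustrative shifts.** The documents give neither p nor γ, so every rate, penalty and correlation here is an assumption. Penalty means WOMAC-PF points added per event. With no shared cause γ equals the penalty; for example, 0.20 × 4 = 0.80.

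The shared-cause columns come from simulation (three runs of 2,000,000). A hidden factor is correlated 0.5 with event liability and 0.5 with WOMAC-PF. A baseline measure correlated 0.7 with that factor is in the model.

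| Penalty | No shared cause, 20% v 10% | No shared cause, 30% v 10% | Shared cause, 20% v 10% | Shared cause, 30% v 10% |
|---|---|---|---|---|
| −4 | +0.40 | +0.80 | +0.21 | +0.44 |
| 0 | 0.00 | 0.00 | −0.19 | −0.37 |
| 2 | −0.20 | −0.40 | −0.39 | −0.77 |
| 4 | −0.40 | −0.80 | −0.59 | −1.17 |
| 7.7 | −0.77 | −1.54 | −0.96 | −1.91 |

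**4. Usual care v one exercise arm.** True benefit 5.2, more events in usual care, 43 v 86, any change in residual SD ignored:
- 5.2 − 0.4 = 4.8: power 91.2%
- 5.2 − 0.8 = 4.4: power 85.9%
- 5.2 − 1.9 = 3.3: power 62.4%

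The last case is extreme: 1.91/0.20 is about 9.5 points between patients with and without an event.

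**5. Clinic v community exercise.** With assumed rates of 10%, 10% and 30% (usual care), a 4-point penalty and the shared cause, this contrast moves by about 0.01 points, while the usual-care contrast moves by about 1.2. The primary contrast moves materially only if the two exercise arms differ in events. If they differed by 20 percentage points with γ = 5, the shift would be 1.0 point. A true 3.3 would become 2.3 (power about 50%) or 4.3, and a true zero would be rejected about 13.5% of the time instead of 5%.

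A separate simulation (4,000 trials, 86 per arm) set the true arm effect to zero. A hidden factor explained 30% of WOMAC-PF variance and raised the log-odds of an event by 1.0 per SD. Adjustment gave −0.44 points and 6.8% rejection when the arm raised the log-odds of an event by 0.7, and −0.93 points and 11.8% when it raised them by 1.4. With no arm effect on events there was no shift.

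**6. Attrition.** As defined, a count per group, it is constant within an arm and cannot be separated from arm in the model. A patient-level indicator needs an observed or imputed score. At the 10% and 15% in the missing-data section, 240 × 0.10 = 24 and 240 × 0.15 = 36. If dropout is permanent, 24 patients have neither score and 36 − 24 = 12 dropouts have a month-3 score. An indicator fitted to those 12, or to imputed data, would still be a post-randomisation adjustment.

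**7. Time window.** No window is set for the adverse-event covariate. Collection runs to month 6, so it could include events that happened after the month-3 endpoint.

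**The case against.** The strongest reply is that the rule never says which outcome analysis it means. Table 1 lists adverse events and attrition under the exploratory aim, and they reappear under the Exploratory Hypothesis, which favours reading the rule as secondary. The Hypothesis 1.1 covariate list is not closed either, since the Data Analysis section already adds baseline adjustments that it does not name. On that view the fault is ambiguity rather than contradiction. The reply fails because the rule is worded as a commitment and nothing limits it to a supportive analysis. The exploratory heading covers the harm measures as outcomes; it says nothing about their use as covariates for function.

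Several other points stand:
- In the scenario the plan predicts, the clinic versus community contrast barely moves.
- Attrition as defined makes the rule unworkable rather than biasing.
- Every size above is assumed, and the 62% power case needs an implausibly strong link for events that are mostly soreness, minor injuries and non-injurious falls.
- The direction is open. The definition of adverse events suggests more in the exercise arms, while the Exploratory Hypothesis expects fewer, so adjustment could inflate or shrink the exercise benefit.

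These points limit the size of the problem without removing it.

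**Conclusion.** The concern holds and should be fixed. The rule in the harms section cannot be squared with an intention-to-treat model built on baseline covariates unless it is deleted or confined to an exploratory analysis. If event rates differ between arms and events are linked to WOMAC-PF, directly or through a shared cause, the adjusted contrast is no longer the intention-to-treat effect.

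The size is unknown. The illustrations give shifts from zero to about 1.9 points, either way depending on the link, and they are not bounds. In the milder cases the test result would seldom change, but the reported effect size would. The usual-care contrasts carry most of the risk. The clinic versus community contrast is at risk only if those two arms differ in events.

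**What to change.** Delete the rule from the Adverse Events paragraph, or say there that any analysis adjusted for harms is exploratory and does not estimate the intention-to-treat effect. Under Hypothesis 1.1, state that the primary outcome model contains no post-randomisation covariate and uses only the baseline covariates listed there, plus any baseline adjustment made under Data Analysis.

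Adverse events and attrition can be reported by arm as the Exploratory Hypothesis section already plans. Dropout is already handled by the mixed model and the missing-data analyses. The cost is one or two sentences, with no extra data or patients and no change to the sample size.

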week during 3 months. The exercise classes offered at these community centers each last approximately 60 minutes, which matches the time of the clinic-based exercise sessions. The supervised group exercise classes for older adults that the subjects will participate consists of a variety of exercises designed to increase general muscular strength, low impact cardiovascular exercise, range of movement, and activity for daily living skills. The participants in these classes are monitored carefully for any signs of physical discomfort and are allowed to rest whenever necessary. No specific body region is targeted with these exercise classes. The goal is to provide participants with strength, balance, and generalized fitness training for the entire body. Some of the specific exercises included in these classes are: partial squats, leg and knee extension/flexion, elastic tubing for strength training of the upper arm and chest muscles, coordination drills with a gym ball such as bouncing, throwing and catching, and cardiovascular exercise using treadmill, bikes or aerobic series on the floor. The classes are taught by physical fitness instructors and are designed specifically for older adults. The instructors are well trained in emergency procedures and are certified in first aid and CPR. The instructors will be briefed on the research design and special needs of patients post TKR. All of the instructors will meet with the principal investigator quarterly for a review of the research protocols.

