We have the support of two of the largest community centers in Pittsburgh that provide these classes and other services to older adults, the Squirrel Hill Jewish Community Center (JCC) and the Vintage Center. These centers will serve as the location sites for this arm of the study. The directors of these centers have agreed to allow us to randomize subjects in this arm of the study to participation in group exercise programs at their facilities. Subjects randomized to this group will be given temporary membership to the Vintage and JCC (see letters of support). These centers are located in two distinct urban settings; the Vintage Center is located in a predominantly low income and African-American neighborhood and the JCC is located in a largely middle-upper income and European-Caucasian neighborhood. Research subjects will be recruited from both of these areas of Pittsburgh and those randomized to this group be given the choice of community center at which they would like to participate in the group exercise classes. Both locations have adequate off-street and metered-street parking, and are located on major mass transit routes.

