Calculations of sample size were based on the primary endpoint of WOMAC-PF at 3 months. We propose to recruit a total of 240 subjects (96 in each exercise arm and 48 in the usual care group) to allow approximately 86 subjects in each exercise arm and 43 in the usual care group available for a complete case analysis at 3 months (assuming 10% attrition at 3 months). We propose a larger number of subjects in both exercises groups (outpatient rehabilitative exercise and community-based group exercise) because we expect a moderate effect size between these two interventions; whereas we propose a smaller number of subjects in the usual care group because we expect a large effect size between the usual medical care group and either of the exercise groups. Thus, with an alpha level of 0.05, 2 tails test, a sample size of 172 (n=86 in each exercise group) will provide 81% power to detect a difference as small as 3.3-point difference between the two exercise groups in WOMAC-PF (SD of 7.7 from our pilot work).¹¹ This would correspond to a difference in less than 2 activities (out of the 17 queried in the WOMAC-PF) having improved from “about moderate difficulty” to “no difficulty”. The sample size of 43 in the usual medical care group will provide 80% power to detect a difference of 5.2-point difference in WOMAC-PF between the usual medical care group and any exercise group. Power analysis was conducted in NCSS/PASS. Moreover, this sample size will provide adequate power (above 80%) to test the hypothesis related to the secondary outcomes (performance-based physical function and physical activity). For example, we will be able to detect differences between the two exercise groups as small as 0.7 sec in the stair climbing test, 0.4 in the chair-rise test, 0.02 m/sec in walking speed, 1.4 sec in the single leg stance, and 35 min/day in light intensity physical activity (based on SD of our own preliminary data). The differences we will be able to detect between the usual care and any intervention groups are as small as 1.01 sec in the stair climbing test, 0.54 in the chair-rise test, 0.03 m/sec in walking speed, 1.6 sec in the

PRINCIPAL INVESTIGATOR (LAST, FIRST, MIDDLE): [name]

single leg stance, and 49 min/day in light intensity physical activity. These differences are smaller than the known minimal detectable changes for these outcomes.⁸⁸⁻⁹⁰

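### The power figure and primary model leave no room for outcome correlation within community classes or instructors; if it exists, the planned standard error for clinic v community is too small

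*Combined protocol and SAP*

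**What the plan says.** **Delivery of the two exercise arms (Interventions).** Community-arm patients join supervised group classes. On who leads them: "The classes are taught by physical fitness instructors and are designed specifically for older adults". On where: "We have the support of two of the largest community centers in Pittsburgh". Patients choose between the two centers. Clinic-arm patients have individual sessions with physical therapists at one research facility. The plan does not give the number of classes, instructors or therapists, or how many trial patients would share one.

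**Sample size (Analytic Methods, Sample Size).** The calculation is made "with an alpha level of 0.05, 2 tails test". It states that "a sample size of 172 (n=86 in each exercise group) will provide 81% power to detect a difference as small as 3.3-point difference", using an "SD of 7.7 from our pilot work". It gives no ICC or design effect.

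**Primary analysis (Data Analysis, Hypothesis 1.1).** The plan uses "contrasts from a linear mixed models analysis for 3 and 6 month function controlling for baseline function" and the randomization covariates, with terms for group and time. The only correlation it describes is between one patient's 3- and 6-month outcomes. The clinic v community contrast at 3 months is named as the main interest. No section mentions clustering by class, instructor, center or therapist, or a sensitivity analysis for it.

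**The concern.** This is a partially nested design: one arm is treated in groups under shared leaders and the other individually. Patients who share an instructor may do better or worse together, because of the instructor's skill, the pace of the class or the company of the others. If so, 86 community patients carry less information about the community program than 86 independent patients. A model with only a patient-level repeated measure does not register this.

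Two things are at stake, and they belong to different tests. If the planned model is used, the nominal 5% test of the main contrast rejects too often. If the clustering is modeled, the 5% level is kept but power is lower. The trial is sized to about 80% power, so it has no margin for either.

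**Working it through.** **Inputs from the plan (Sample Size).** Recruitment of "96 in each exercise arm and 48 in the usual care group", "assuming 10% attrition at 3 months": 96 × 0.9 = 86.4, taken as 86 per exercise arm. Difference 3.3 points, SD 7.7, two-sided alpha 0.05.

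**Step 1: the plan's own figure.** SE = 7.7 × √(2/86) = 1.174. Then 3.3/1.174 = 2.810, and power = Φ(2.810 − 1.960) = Φ(0.850) = 80.2% (79.8% with the t distribution). This agrees with the stated 81% to within rounding of its inputs. The formula treats all patients as independent.

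**Step 2: clustering in the community arm only.** The inputs here are assumptions: m = 3 to 20 trial patients per class or instructor, and ICC = 0.01 to 0.05. Total SD is held at 7.7 and taken as the residual SD.

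- Design effect in the community arm: DE = 1 + (m − 1) × ICC
- Correct standard error: SE* = 7.7 × √[(1 + DE)/86]
- Planned test, type I error: 2 × [1 − Φ(1.960 × 1.174/SE*)]
- Planned test, power: Φ[(3.3 − 1.960 × 1.174)/SE*]
- Power of a test that uses SE*: Φ(3.3/SE* − 1.960)

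Worked example, m = 20 and ICC 0.05: DE = 1.95, and SE* = 7.7 × √(2.95/86) = 1.426. Type I error = 2 × [1 − Φ(1.614)] = 10.7%. Planned-test power = Φ(0.700) = 75.8%. Power with clustering allowed for = Φ(2.314 − 1.960) = 63.8%.

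| m | ICC | DE | SE*/SE | Planned test: type I error | Planned test: power | Clustering allowed for: power |
|---|---|---|---|---|---|---|
| any | 0 | 1.00 | 1.00 | 5.0% | 80.2% | 80.2% |
| 3 | 0.01 | 1.02 | 1.005 | 5.1% | 80.1% | 79.8% |
| 3 | 0.02 | 1.04 | 1.01 | 5.2% | 80.0% | 79.5% |
| 10 | 0.02 | 1.18 | 1.04 | 6.0% | 79.2% | 76.8% |
| 10 | 0.05 | 1.45 | 1.11 | 7.7% | 77.9% | 71.9% |
| 20 | 0.02 | 1.38 | 1.09 | 7.2% | 78.2% | 73.1% |
| 20 | 0.05 | 1.95 | 1.21 | 10.7% | 75.8% | 63.8% |

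**Step 3: check by simulation.** With 20,000 simulated null trials per setting and ICC 0.05, the unadjusted test rejected in 7.7% with 8 classes (86/8 ≈ 11 per class) and in 11.0% with 4 (86/4 ≈ 22). Both fit the table.

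**Step 4: few clusters.** The last column uses the normal approximation. Satterthwaite degrees of freedom lower it further: at m = 10 and ICC 0.05, from 71.9% to 67.8%.

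**The case against.** **The correlation may be negligible.** The plan describes existing center programs joined through temporary membership, and patients are randomized one at a time. It describes no closed cohorts of trial patients, so few may share a class. With m = 3 and ICC 0.01, type I error is 5.1% and almost no power is lost. This stands, and it is why the point is conditional. A reader might infer that the error bars are certainly too narrow or that type I error is known to exceed 5%. The documents do not show that, because they give neither ICC nor cluster size.

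**Baseline adjustment may restore the power.** The model adjusts for baseline function and other covariates, and the plan does not say whether 7.7 is an adjusted SD. If it is unadjusted, an assumed baseline correlation of 0.5 would cut variance by 25%. That more than offsets the variance inflation (1 + DE)/2 of 1.09 to 1.19 at ICC 0.02 and m = 10-20. So the documents do not establish that true power is below 81%. Adjustment does not correct the type I error of a model that ignores clustering.

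**Clustering by center would look much worse.** With 43 patients at each center and ICC 0.02, the planned test's type I error would be 10.0%. That scenario should not be relied on. Patients choose their center, and the two neighborhoods differ in income and race, so similarity within a center may be patient mix rather than a treatment effect.

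**The conclusion could be limited to these classes and instructors.** The extra variance would then not apply. But the Design Overview stresses generalizability, and the Community-based group exercise section seeks evidence for payers and policy makers on prescribing such programs. Both point to a wider conclusion.

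**Conclusion.** The omission is confirmed in both the power calculation and the model, and it falls on the contrast of primary interest. The direction is clear for any positive class or instructor ICC; the size is not.

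Under the assumed ICC 0.01-0.05 and 3-20 trial patients per class or instructor:

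- The planned test has type I error of 5.1-10.7% and power of about 80-76%.
- A test that allows for the clustering keeps 5% and has power of about 80-64% by the normal approximation, less with small-sample degrees of freedom.

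The two power ranges belong to different tests. It would be wrong to read 10.7% and 64% as properties of one analysis. Both ranges should be compared with 80.2% at ICC 0 and take 7.7 as the residual SD. They leave out any clustering by therapist in the clinic arm, which would add to the variance.

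This is an inexpensive improvement to the plan, not a demonstrated error in the primary result.

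**What to change.** 1. **Record membership.** Note each community patient's main class and instructor, and each clinic patient's therapist, with the attendance data already planned. The plan does not say that the centers' reports identify class or instructor, so the field has to be requested. It may not be recoverable later.
2. **Prespecify a partially nested mixed model** for the 3-month clinic v community contrast, at least as a sensitivity analysis. Include a random effect for main instructor or class in the community arm, and for therapist in the clinic arm if several treat. Use small-sample degrees of freedom. State a rule for patients who attend more than one class, since nothing ties a patient to one. Do not fit a random effect for the two centers: two units cannot support it, and patients select their center.
3. **Amend the power statement** to say that 81% assumes zero ICC, and give the range above with its assumptions.

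The cost is a data field in each exercise arm and one or two model terms. Intervals will be slightly wider, and with few clusters the variance component will be imprecise. Even with that component estimated at zero, the small-sample degrees of freedom mean that this model need not return exactly the planned result.
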